4.2.4.2 Axitinib

Axitinib will be administered at the standard dosing of 5mg po twice daily.

^a For patients with liver metastasis who begin treatment with Grade 2 AST or ALT, if AST or ALT increases by greater than or equal to 50% relative to baseline and lasts for at least 1 week then patients should be discontinued.

b If symptoms resolve within one hour of stopping drug infusion, the infusion may be restarted at 50% of the original infusion rate (e.g., from 100 mL/hr to 50 mL/hr). Otherwise dosing will be held until symptoms resolve and the subject should be premedicated for the next scheduled dose; Refer to Table 5– Infusion Treatment Guidelines for further management details.

c Patients with intolerable or persistent Grade 2 drug-related AE may hold study medication at physician discretion. Permanently discontinue study drug for persistent Grade 2 adverse reactions for which treatment with study drug has been held, that do not recover to Grade 0-1 within 12 weeks of the last dose.

Table 4. Axitinib Dose Modification Guidelines for Drug-Related Adverse Events

Toxicity	Action	
Grade 4 non-hematologic toxicity considered related to axitinib per investigator judgment (including persistent nausea, vomiting, diarrhea, hypertension despite optimal medical therapy), excluding clinically manageable laboratory abnormalities (e.g. electrolytes).	Discontinue axitinib.	
Grade 3 non-hematologic toxicity considered related to axitinib per investigator judgment (including persistent nausea, vomiting, diarrhea, hypertension, proteinuria despite optimal medical therapy), excluding clinically manageable laboratory abnormalities (e.g. electrolytes).	Hold axitinib until recovery to Grade 0-1 or baseline and resume at the same dose level. If grade 3 toxicity reoccurs despite reduction, patient may be dose reduced by 1 dose level upon recovery to Grade 0-1 or baseline. Prompt palliative and supportive measures mandated per local standard of care (eg, antiemetic).	
Grade 3 Thrombocytopenia, ie, PLTS <50,000 mm3 (50.0 x 109/L) with bleeding.	Discontinue Axitinib	
Grade 3 hematologic toxicity considered related to axitinib per investigator judgment	 -Hold axitinib until recovery to Grade ≤ 2 or baseline and resume axitinib at the same dose level. -If grade 3 toxicity reoccurs, patient may either be held until recovery and continued at same dose, or undergo dose reduction by 1 dose level. 	
Grade 4 toxicity considered related to axitinib per investigator judgment	Discontinue Axitinib	
No recovery of toxicities within 6 weeks to grade 0 or grade 1	Discontinue Axitinib	

Table 5. Axitinib Dose Levels

Dose Level	Dose
Level 0 (starting dose)	5 mg po bid
Level -1	3 mg po bid
Level -2	2 mg po bid

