4.2.5 Timing of Dose Administration

Nivolumab: Trial treatment should be administered on Day 1 of each cycle after all procedures/assessments have been completed as detailed on the Trial Flow Chart (Section 6.0). Trial treatment may be administered up to 3 days before or after the scheduled Day 1 of each cycle due to administrative reasons.

All trial treatments will be administered on an outpatient basis.

Nivolumab 480 mg will be administered as a 30 minute IV infusion every 4 weeks. Sites should make every effort to target infusion timing to be as close to 30 minutes as possible. However, given the variability of infusion pumps from site to site, a window of -5 minutes and +10 minutes is permitted (i.e., infusion time is 30 minutes: -5 min/+10 min).

Nivolumab will be prepared and infused per institutional standards

Axitinib: Axitinib 5 mg PO twice daily, 12 hours apart, will be taken for the entire duration of treatment. Patients will be given specific instructions on how to take axitinib. If a dose is missed, it may be taken up to 8 hours later that same day.

Dosing interruptions of nivolumab and axitinib are permitted in the case of medical / surgical events or logistical reasons not related to study therapy (e.g., elective surgery, unrelated medical events, patient vacation, and/or holidays). Subjects should be placed back on study therapy within 3 weeks of the scheduled interruption, unless otherwise discussed with the Sponsor. The reason for interruption should be documented in the patient's study record.

Should the combination of nivolumab and axitinib be further investigated for the treatment of anti-PD1 refractory melanoma, given the potential for late onset immune-related toxicities for nivolumab, any such late toxicity will be considered in the determination of the final dose and dose schedule. The number of required dose reductions of axitinib will also be taken into full consideration.

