4.5 Subject Withdrawal/Discontinuation Criteria

Subjects may withdraw consent at any time for any reason or be dropped from the trial at the discretion of the investigator should any untoward effect occur. In addition, a subject may be withdrawn by the investigator or the Sponsor if enrollment into the trial is inappropriate, the trial plan is violated, or for administrative and/or other safety reasons.

A subject must be discontinued from the trial for any of the following reasons:

- The subject or legal representative (such as a parent or legal guardian) withdraws consent.
- Confirmed radiographic disease progression

Note: For unconfirmed radiographic disease progression, please see Section 5.2.2

Note: A subject may be granted an exception to continue on treatment with confirmed radiographic progression if clinically stable or clinically improved, please see Section 7.1.2.7.1

- Unacceptable adverse experiences as described in Section 5.2.1.2
- Intercurrent illness that prevents further administration of treatment
- Investigator's decision to withdraw the subject
- The subject has a confirmed positive serum pregnancy test
- Noncompliance with trial treatment or procedure requirements
- The subject is lost to follow-up
- Completed 24 months of uninterrupted treatment with nivolumab or 24 administrations of study medication, whichever is later.

Note: 24 months of study medication is calculated from the date of first dose.

• After trial discontinuation (whether due to subject withdrawal, progression, or dose limiting toxicity), patients will be seen at week 4 for follow up, and then followed once 100 days after the last day of treatment even if they start a new anticancer therapy. Patients will be contacted by phone for survival follow up for up to 5 years.

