5.2 Assessing and Recording Adverse Events

An adverse event is defined as any untoward medical occurrence in a patient or clinical investigation subject administered a pharmaceutical product and which does not necessarily have to have a causal relationship with this treatment. An adverse event can therefore be any unfavorable and unintended sign (including an abnormal laboratory finding, for example), symptom, or disease temporally associated with the use of a medicinal product or protocol-specified procedure, whether or not considered related to the medicinal product or protocol-specified procedure. Any worsening (i.e., any clinically significant adverse change in frequency and/or intensity) of a preexisting condition that is temporally associated with the use of the treatments agents, is also an adverse event.

All adverse events that occur after the consent form is signed but before treatment allocation/randomization must be reported by the investigator if they cause the subject to be excluded from the trial, or are the result of a protocol-specified intervention, including but not limited to washout or discontinuation of usual therapy, diet, placebo treatment or a procedure.

From the time of treatment allocation/randomization through 100 days following cessation of treatment, or until the participant initiates new anticancer therapy, whichever is earlier, all adverse events must be reported by the investigator. Such events will be recorded at each examination on the Adverse Event case report forms/worksheets. The reporting timeframe for adverse events meeting any serious criteria is described in section 7.2.3.1. The investigator will make every attempt to follow all subjects with non-serious adverse events for outcome.

Adverse events will not be collected for subjects during the pre-screening period (for determination of archival tissue status) as long as that subject has not undergone any protocol-specified procedure or intervention. If the subject requires a blood draw, fresh tumor biopsy etc., the subject is first required to provide consent to the main study and AEs will be captured according to guidelines for standard AE reporting.

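### Axitinib Table 4: the Grade 3 non-hematologic row ties a dose reduction to one that has not been ordered, and the six-week stop row leaves out the return-to-baseline alternative

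*Combined protocol and SAP*

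**What the plan says.** All the rules are in protocol section 4.2.4.2 (Axitinib), Table 4. Table 5 gives the dose levels: 5 mg, 3 mg and 2 mg, each twice daily.

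- **Grade 3 non-hematologic, first event:** "Hold axitinib until recovery to Grade 0-1 or baseline and resume at the same dose level".
- **Grade 3 non-hematologic, recurrence:** "If grade 3 toxicity reoccurs despite reduction, patient may be dose reduced by 1 dose level", once toxicity has again recovered to Grade 0-1 or baseline.
- **Grade 3 hematologic, first event:** "Hold axitinib until recovery to Grade ≤ 2 or baseline and resume axitinib at the same dose level".
- **Grade 3 hematologic, recurrence:** "If grade 3 toxicity reoccurs, patient may either be held until recovery and continued at same dose, or undergo dose reduction" by one level.
- **Six-week row:** axitinib is discontinued if there is "No recovery of toxicities within 6 weeks to grade 0 or grade 1".

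Section 4.3.1 (Supportive Care Guidelines) sends the reader back to section 4.2.4.2 for axitinib toxicities and adds no rule on either point. On any later choice of dose for the combination, section 4.2.5 says: "The number of required dose reductions of axitinib will also be taken into full consideration".

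**The concern.** Table 4 is the working rule for toxicity of one of the two study drugs, so each row should give one answer for each situation it covers. Two rows do not.

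The Grade 3 non-hematologic row makes a reduction depend on an earlier reduction, yet its only earlier instruction is to resume at the dose the patient was already taking. This row covers the toxicities the table itself names: nausea, vomiting, diarrhea, hypertension and proteinuria.

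The six-week row names only Grades 0 and 1. For a patient who entered above Grade 1, the two Grade 3 rows and the six-week row can point in opposite directions.

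Three things are at stake: consistent axitinib dosing across patients, the count of axitinib stops, and the count of dose reductions that section 4.2.5 says will be weighed. A site that follows the likely intent departs from the written protocol. A site that follows the text may skip a reduction or stop a drug without need.

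**Working it through.** The documents give no figure to reproduce here. The check is a trace through the rows, with one small sum for the dose.

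**(a) Recurrent Grade 3 non-hematologic toxicity**

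1. The patient starts at Level 0, 5 mg twice daily (Table 5).
2. At the first Grade 3 event, axitinib is held and, after recovery, resumed at 5 mg twice daily. No reduction has taken place.
3. At the second Grade 3 event, the condition in the row is recurrence despite a reduction. The patient is still at Level 0, so the condition is false.
4. Read literally, the row therefore offers no valid step to Level -1 at a first recurrence.
5. In the hematologic row, recurrence alone is the trigger, so the same sequence reaches Level -1. Two rows of Table 4 mention dose reduction, and only this one can produce a first reduction as written.

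Dose involved: Level 0 is 5 mg × 2 = 10 mg/day and Level -1 is 3 mg × 2 = 6 mg/day. (10 − 6)/10 = 40% lower.

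**(b) The six-week row for a patient with a Grade 2 baseline**

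1. Such patients can be enrolled. Section 4.1.1, Table 1, allows AST/ALT up to 5 times the upper limit of normal with liver metastases, and footnote a to Table 3 speaks of patients with liver metastasis who start treatment at Grade 2 AST or ALT. The first note to exclusion 11 in section 4.1.2 admits patients with neuropathy up to Grade 2.
2. Suppose such a patient has a Grade 3 worsening attributed to axitinib. The drug is held, the toxicity returns to Grade 2 before week six, and that is baseline. The non-hematologic row allows restart.
3. At six weeks the toxicity is still Grade 2. The six-week row requires Grade 0 or 1 and does not mention baseline, so read literally axitinib is discontinued.

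| State at six weeks | Grade 3 row | Six-week row |
|---|---|---|
| Grade 0-1, either toxicity type | restart allowed | no stop |
| Non-hematologic Grade 2, baseline Grade 0-1 | restart not allowed | stop (consistent) |
| Grade 2 that equals baseline | restart allowed | stop (conflict) |
| Hematologic Grade 2, baseline Grade 0-1 | restart allowed | stop (intent not stated) |

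The third line is the gap. The fourth is a question of intent, taken up under the objection. The table lists situations and says nothing about how often they occur.

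**The case against.** The strongest reply on (a) is that the row says the dose *may* be reduced, in a table headed as guidelines, and nothing forbids a reduction at other times. Table 5 sets lower levels, section 4.2.5 expects reductions, and a sensible investigator would read the phrase as recurrence despite the hold. The sentence also works for a patient already reduced under the hematologic row. All of this lowers the severity. It does not make the stated trigger correct for a patient still at 5 mg twice daily, and no other section supplies the missing step.

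A reader might infer from (a) that patients are kept on a toxic dose. The documents do not support that. Holding and supportive care are in the same row, Grade 4 non-hematologic toxicity stops the drug (manageable laboratory abnormalities apart), and section 4.5 lists the investigator's "decision to withdraw the subject" as a ground for discontinuation.

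On (b), a reader might infer that the six-week row cancels the table's restart thresholds altogether. It does not. It agrees with the Grade 0-1 threshold, and it does not block a restart at Grade 2 before week six. For hematologic toxicity the two rules can operate together: one says when dosing may resume, the other sets an outer limit for fuller recovery. Nivolumab has a similar limit in footnote c to Table 3, which stops drug for held, persistent Grade 2 reactions that have not reached Grade 0-1 within 12 weeks. Calling the hematologic Grade 2 stop an error, and relaxing it, would loosen a safety rule that may be deliberate.

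Section 5.2 also helps the sponsor. It counts as an adverse event "Any worsening (i.e., any clinically significant adverse change in frequency and/or intensity) of a preexisting condition", so return to baseline could be taken as recovery. That is probably what is meant, but the six-week row names grades and does not say so, whereas both Grade 3 rows mention baseline explicitly.

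The platelet entry limit of 50,000 might look like a further example. Table 4 shows only that Grade 3 lies below that count. The grading scale is not reproduced, so the example is not needed and is not relied on.

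**Conclusion.** Table 4 has one rule that is wrong as written and one that is incomplete. Both are low in severity and worth correcting.

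(a) The trigger for reduction in the Grade 3 non-hematologic row cannot be met at a first recurrence in a patient who resumed at the starting dose. This rests only on the row's own wording, and confidence is high. The step at issue is 10 versus 6 mg/day.

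(b) The six-week row lacks the baseline alternative that both Grade 3 rows carry. The conflict arises for patients who enter at Grade 2, for which AST/ALT with liver metastases and neuropathy are documented examples. It assumes that the worsening is attributed to axitinib and, for AST/ALT, that it is not set aside as a manageable laboratory abnormality. If return to baseline is already understood as recovery, the gap is one of wording only.

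The treatment of hematologic Grade 2 at six weeks in a patient with a lower baseline is an open question of intent and not a demonstrated error.

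The number of patients affected cannot be derived from the documents. The sample size of 31, the stated error rates and the response analysis are unaffected.

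**What to change.** 1. In the Grade 3 non-hematologic row, make the trigger recurrence after resumption, in line with the hematologic row.
2. In the six-week row, add baseline as a third acceptable state beside Grades 0 and 1.
3. Ask the sponsor to decide and state whether hematologic Grade 2 from a lower baseline should stop axitinib at six weeks, given that restart is allowed at Grade 2 or below. Until that is decided, leave the stop in place.

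Two clarifications can go in at the same time, though the point does not depend on them. The later Grade 4 row probably means hematologic toxicity and could say so. Table 9 in section 7.1 lists only 5 mg tablets, while Table 5 needs 3 mg and 2 mg doses (3/5 = 0.6 and 2/5 = 0.4 of a tablet), so a suitable strength could be listed.

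Cost: a few words in two rows and one sponsor decision. The clarifications add a word or phrase in a third row and one entry in Table 9. Sample size, visits and analysis do not change.

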4.2.5 Timing of Dose Administration

Nivolumab: Trial treatment should be administered on Day 1 of each cycle after all procedures/assessments have been completed as detailed on the Trial Flow Chart (Section 6.0). Trial treatment may be administered up to 3 days before or after the scheduled Day 1 of each cycle due to administrative reasons.

All trial treatments will be administered on an outpatient basis.

Nivolumab 480 mg will be administered as a 30 minute IV infusion every 4 weeks. Sites should make every effort to target infusion timing to be as close to 30 minutes as possible. However, given the variability of infusion pumps from site to site, a window of -5 minutes and +10 minutes is permitted (i.e., infusion time is 30 minutes: -5 min/+10 min).

Nivolumab will be prepared and infused per institutional standards

Axitinib: Axitinib 5 mg PO twice daily, 12 hours apart, will be taken for the entire duration of treatment. Patients will be given specific instructions on how to take axitinib. If a dose is missed, it may be taken up to 8 hours later that same day.

Dosing interruptions of nivolumab and axitinib are permitted in the case of medical / surgical events or logistical reasons not related to study therapy (e.g., elective surgery, unrelated medical events, patient vacation, and/or holidays). Subjects should be placed back on study therapy within 3 weeks of the scheduled interruption, unless otherwise discussed with the Sponsor. The reason for interruption should be documented in the patient's study record.

Should the combination of nivolumab and axitinib be further investigated for the treatment of anti-PD1 refractory melanoma, given the potential for late onset immune-related toxicities for nivolumab, any such late toxicity will be considered in the determination of the final dose and dose schedule. The number of required dose reductions of axitinib will also be taken into full consideration.

4.2.6 Trial Blinding/Masking

This is an open-label trial; therefore, the Sponsor, investigator and subject will know the treatment administered.

4.3 Rescue Medications & Supportive Care

4.3.1 Supportive Care Guidelines

Subjects should receive appropriate supportive care measures as deemed necessary by the treating investigator. Suggested supportive care measures for the management of adverse events with potential immunologic etiology are outlined below. Where appropriate, these guidelines include the use of oral or intravenous treatment with corticosteroids as well as additional anti-inflammatory agents if symptoms do not improve with administration of corticosteroids. Note that several courses of steroid tapering may be necessary as symptoms may worsen when the steroid dose is decreased. For each disorder, attempts should be made to rule out other causes such as metastatic disease or bacterial or viral infection, which might require additional supportive care. The treatment guidelines are intended to be applied when the investigator determines the events to be related to study drug(s).

Note: if after the evaluation the event is determined not to be related, the investigator does not need to follow the treatment guidance (as outlined below). Refer to Section 4.2.4 for dose modification.

It may be necessary to perform conditional procedures such as bronchoscopy, endoscopy, or skin photography as part of evaluation of the event.

For toxicities where the attribution is Nivolumab (immune mediated toxicity)

• Pneumonitis:

- For Grade 2 events, treat with systemic corticosteroids. When symptoms improve to Grade 1 or less, steroid taper should be started and continued over no less than 4 weeks.
- For Grade 3-4 events, immediately treat with intravenous steroids.
 Administer additional anti-inflammatory measures, as needed.
- o Add prophylactic antibiotics for opportunistic infections in the case of prolonged steroid administration.

• Diarrhea/Colitis:

Subjects should be carefully monitored for signs and symptoms of enterocolitis (such as diarrhea, abdominal pain, blood or mucus in stool, with or without fever) and of bowel perforation (such as peritoneal signs and ileus).

- All subjects who experience diarrhea/colitis should be advised to drink liberal quantities of clear fluids. If sufficient oral fluid intake is not feasible, fluid and electrolytes should be substituted via IV infusion. For Grade 2 or higher diarrhea, consider GI consultation and endoscopy to confirm or rule out colitis.
- o For **Grade 2 diarrhea/colitis**, administer oral corticosteroids.
- For Grade 3 or 4 diarrhea/colitis, treat with intravenous steroids followed by high dose oral steroids.
- O When symptoms improve to Grade 1 or less, steroid taper should be started and continued over no less than 4 weeks.
- Type 1 diabetes mellitus (if new onset, including diabetic ketoacidosis [DKA]) or ≥ Grade 3 Hyperglycemia, if associated with ketosis (ketonuria) or metabolic acidosis (DKA)
 - o For **T1DM** or **Grade 3-4** Hyperglycemia
 - Insulin replacement therapy is recommended for Type I diabetes mellitus and for Grade 3-4 hyperglycemia associated with metabolic acidosis or ketonuria.

• Evaluate patients with serum glucose and a metabolic panel, urine ketones, glycosylated hemoglobin, and C-peptide.

• Hypophysitis:

- For Grade 2 events, treat with corticosteroids. When symptoms improve to Grade 1 or less, steroid taper should be started and continued over no less than 4 weeks. Replacement of appropriate hormones may be required as the steroid dose is tapered.
- o For **Grade 3-4** events, treat with an initial dose of IV corticosteroids followed by oral corticosteroids. When symptoms improve to Grade 1 or less, steroid taper should be started and continued over no less than 4 weeks. Replacement of appropriate hormones may be required as the steroid dose is tapered.

• Hyperthyroidism or Hypothyroidism:

Thyroid disorders can occur at any time during treatment. Monitor patients for changes in thyroid function (at the start of treatment, periodically during treatment, and as indicated based on clinical evaluation) and for clinical signs and symptoms of thyroid disorders.

- o **Grade 2** hyperthyroidism events (and **Grade 2-4** hypothyroidism):
 - In hyperthyroidism, non-selective beta-blockers (e.g. propranolol) are suggested as initial therapy.
 - In hypothyroidism, thyroid hormone replacement therapy, with levothyroxine or liothyroinine, is indicated per standard of care.

Grade 3-4 hyperthyroidism

Treat with an initial dose of IV corticosteroid followed by oral corticosteroids. When symptoms improve to Grade 1 or less, steroid taper should be started and continued over no less than 4 weeks. Replacement of appropriate hormones may be required as the steroid dose is tapered.

• Hepatic:

- For **Grade 2** events, monitor liver function tests more frequently until returned to baseline values (consider weekly).
 - Treat with IV or oral corticosteroids
- o For **Grade 3-4** events, treat with intravenous corticosteroids for 24 to 48 hours.
- O When symptoms improve to Grade 1 or less, a steroid taper should be started and continued over no less than 4 weeks.

• Renal Failure or Nephritis:

- o For **Grade 2** events, treat with corticosteroids.
- o For **Grade 3-4** events, treat with systemic corticosteroids.
- When symptoms improve to Grade 1 or less, steroid taper should be started and continued over no less than 4 weeks.
- Management of Infusion Reactions: Signs and symptoms usually develop during or shortly after drug infusion and generally resolve completely within 24 hours of completion of infusion.

Table 6 below shows treatment guidelines for subjects who experience an infusion reaction associated with administration of nivolumab.

Table 6: Infusion Reaction Treatment Guidelines

NCI CTCAE Grade	Treatment	Premedication at subsequent dosing
Grade 1 Mild reaction; infusion interruption not indicated; intervention not indicated	Increase monitoring of vital signs as medically indicated until the subject is deemed medically stable in the opinion of the investigator.	None
Grade 2 Requires infusion interruption but responds promptly to symptomatic treatment (e.g., antihistamines, NSAIDS, narcotics, IV fluids); prophylactic medications indicated for < =24 hrs	Stop Infusion and monitor symptoms. Additional appropriate medical therapy may include but is not limited to: IV fluids Antihistamines NSAIDS Acetaminophen Narcotics Increase monitoring of vital signs as medically indicated until the subject is deemed medically stable in the opinion of the investigator. If symptoms resolve within one hour of stopping drug infusion, the infusion may be restarted at 50% of the original infusion rate (e.g., from 100 mL/hr to 50 mL/hr). Otherwise dosing will be held until symptoms resolve and the subject should be premedicated for the next scheduled dose. Subjects who develop Grade 2 toxicity despite adequate premedication should be permanently discontinued from further trial	Subject may be premedicated 1.5h (± 30 minutes) prior to infusion of with: Diphenhydramine 50 mg po (or equivalent dose of antihistamine). Acetaminophen 500-1000 mg po (or equivalent dose of antipyretic).
C12 A	treatment administration.	No subsequent desires
Grades 3 or 4 Grade 3: Prolonged (i.e., not rapidly responsive to symptomatic medication and/or brief interruption of infusion); recurrence of symptoms following initial improvement; hospitalization indicated for other clinical sequelae (e.g., renal impairment, pulmonary infiltrates)	Stop Infusion. Additional appropriate medical therapy may include but is not limited to: IV fluids Antihistamines NSAIDS Acetaminophen Narcotics Oxygen Pressors Corticosteroids Epinephrine	No subsequent dosing
Grade 4: Life-threatening; pressor or ventilatory support indicated	Increase monitoring of vital signs as medically indicated until the subject is deemed medically stable in the opinion of the investigator. Hospitalization may be indicated.	

NCI CTCAE Grade	Treatment	Premedication at subsequent dosing					
	Subject is permanently discontinued from						
	further trial treatment administration.						
Appropriate resuscitation equipment she administration.	ould be available in the room and a physician readily	y available during the period of drug					

For toxicities where the attribution is Axitinib (non-immune mediated toxicity)

Dose modifications as in Section 4.2.4.2. Management of hypertension and febrile neutropenia per investigator.

